9.6 Efficacy Analyses

This section addresses the analyses to be conducted on the primary, secondary, and exploratory efficacy variables.

The efficacy analysis will be carried out using the patients from the FAS. Figures for selected efficacy endpoints, such as the primary pruritus endpoint, change in serum bile acids, and change in other patient-reported and caregiver-reported outcomes, will be provided by cohort/treatment subgroup and by visit. Forest plots will be provided for the efficacy subgroup analyses.

For efficacy endpoints derived from central laboratory data, if central laboratory data are not available due to COVID-19 or other reasons, local laboratory data will be used and converted to standard unit used by central laboratory. In addition, laboratory related efficacy endpoints will only be considered up to 14 days follow-up after the last dose.

9.6.1 Analysis Methods

Descriptive statistics mainly will be used in this open-label extension study unless otherwise specified.

9.6.2 Treatment by Centre Interaction Analysis (Multicentre Study)

NA

9.6.3 Analyses of Primary Efficacy Endpoints

All the primary analyses will be based on the FAS, unless otherwise specified.

For the EU and RoW, change from baseline 2 in fasting serum bile acids will be analysed by using the 1-sample t-test or the Wilcoxon signed rank test, as appropriate at the end of the 72-week treatment period based on the average of the values at Weeks 70 and 72. Baseline 2, defined in the table of derived variables in [Appendix A](#), will be used to calculate change from baseline for the summary.

For Cohort 1 patients who were on odevixibat in Study A4250-005, change from Baseline 1 to end of the 72-week treatment in Study A4250-008 will be analysed by using the 1-sample t-test or the Wilcoxon signed rank test, as appropriate. Baseline 1,

defined in the table of derived variables in [Appendix A](#), will be used for this statistical analysis.

For the US, the proportion of positive pruritus assessments at the patient level over the 72-week treatment period using the Albireo ObsRO instrument will be summarised descriptively. A positive pruritus assessment is defined as a scratching score of ≤ 1 or at least a 1-point drop from baseline on the Albireo ObsRO instrument. At each assessment, the AM score will be compared to the baseline AM average, and the PM score will be compared to the baseline PM average. Both AM and PM pruritus assessments will be included in the analysis of this endpoint. For analysis purposes, diary entries will be assigned to a study day based on the recorded date regardless of recorded time. AM scores from the period of 14 days before or on the first dose day in Study A4250-008 will be averaged as AM baseline. PM scores from the period of 14 days before the first dose day in Study A4250-008 will be averaged as PM baseline. If a patient's baseline score is ≤ 1 , then only the criterion of a one-point drop from baseline on the Albireo ObsRO instrument will be used to determine whether a pruritus assessment is positive or not for the primary endpoint analysis. Rounded baseline score will be used for the analysis.

A 95% CI will be provided for the proportion of positive pruritus assessments.

Change from Baseline 1 and 2 in monthly scratching severity score to end of the 72-week treatment in Study A4250-008 will be analysed by using the 1-sample t-test or the Wilcoxon signed rank test, as appropriate. Baseline 1 will only be used for patients in Cohort 1 who were on odevixibat in Study A4250-005.

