Before protocol amendment 6 of the A4250-008 protocol, eligible patients were enrolled into this open-label extension study and treated with a daily dose of odevixibat 120 µg/kg/day for 72 weeks. Patients not tolerating the 120 µg/kg/day dose after a minimum of 1 week had the option to down-titrate to a lower dose (40 µg/kg/day). The patient was to return to the higher dose as soon as deemed appropriate by the investigator. Under protocol amendment 6, patients entering Cohort 2 were to start treatment at 40 µg/kg/day with the possibility to dose escalate to 120 µg/kg/day after 12 weeks if there was no improvement in pruritus based on investigator judgment. The patient could return to the lower dose if the 120 µg/kg/day dose was not tolerated following a minimum of 1 week of treatment. Any dose titration was to be done in consultation with the sponsor Medical Monitor or designee. Patients who wished to continue receiving odevixibat after 72 weeks had the option to remain on treatment in an extension period with visits every 16 weeks until the drug was commercially available, provided continued use was supported by the risk-benefit profile and the patient had not been previously withdrawn or discontinued from the study. In that case the 4-week Follow-up period would not occur.

Patients in Cohort 2 went through a Screening period consisting of 2 clinic visits as follows:

[figure not shown]
- Visit S-1: Screening Visit 1 (Days -56 to -35)
- Visit S-2: Screening Visit 2 (Days -28 to -7)

Patients who did not meet eligibility criteria may have been re-screened after consultation with the Medical Monitor. Patients not fulfilling inclusion/exclusion criteria after 3 attempts were not allowed to rescreen.

All patients were to have a minimum of 12 clinic visits and 6 scheduled telephone contacts (see [Figure 1](#) and [Figure 2](#)) as follows:

- Visit 1: Screening/inclusion visit (Day 1; coincided with Visit 9/End of Treatment (EOT) in Study A4250-005 for patients in Cohort 1. Assessments that were performed at Visit 9/EOT during Study A4250-005 were not to be repeated.)
- Visit 2: Week 4
 - Telephone contact 1: Week 8
- Visit 3: Week 12
 - Telephone contact 2: Week 18
- Visit 4: Week 22
- Visit 5: Week 24
 - Telephone contact 3: Week 30
- Visit 6: Week 36
 - Telephone contact 4: Week 42
- Visit 7: Week 46
- Visit 8: Week 48
 - Telephone contact 5: Week 54
- Visit 9: Week 60
 - Telephone contact 6: Week 66
- Visit 10: Week 70

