If a patient was prematurely withdrawn from the study prior to Week 72, all assessments scheduled for Visit 11 were to be performed at the time the patient withdrew. If a patient participating in the optional extension study withdrew prior to commercial drug availability, all assessments scheduled for the optional extension period EOT visit were to be performed.

If a liver biopsy was performed according to the local regulations or standard of care at any time during A4250-008, the biopsy results should have been recorded in the electronic case report form (eCRF). If liver biopsy results were collected for a patient in Study A4250-005 or prior to Week 24 in Study A4250-008, the patient was to be asked to consent to a follow-up liver biopsy at Visit 11, if allowed per local regulations, unless 2 prior liver biopsy results had been collected (with at least 1 year between biopsies). Liver biopsies were not performed in Spain.

For patients not participating in the optional extension period, Visit 12 was to take place 28 days after Visit 11. All patients who were prematurely withdrawn were to have this visit 28 days after the last dose of study drug for AE monitoring and other safety follow-up assessments.

If a patient discontinued before Week 72, additional telephone contacts were to be made every 3 months after the Follow-up visit (Visit 12) up to Week 72 to inquire whether the patient had undergone biliary diversion or liver transplantation, and if ongoing TEAEs at the time of discontinuation had resolved. The telephone calls were to take place up until 72 weeks even if the patient had biliary diversion or liver transplant.

Patients and/or caregivers were instructed to complete the electronic diary (eDiary) every morning and evening for the first 24 weeks (Visits 1 to 5) and for the 21 days before each clinic visit thereafter (Visits 6 to 12). In addition, Cohort 2 patients and/or caregivers were instructed to complete the eDiary during the Screening period. Patients participating in the optional extension period were not to complete eDiary entries after Visit 11. The eDiary included patient-reported outcome (PRO) and observer reported outcome (ObsRO) items for evaluation of itching (using PRO), scratching (using ObsRO), and

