	The number of capsules planned to be taken will be estimated based on patient's body weight per Protocol Table 3. If a patient's weight changes at any time during the study, dose adjustment will be required.
Derivations for Efficacy Parameters	
Baseline (general)	
Baseline 1 is defined as the last value prior to the first dose in Study A4250-005 for patients in Cohort 1.
 
Baseline 2 is defined as the last value prior to the first dose in Study A4250-008 for all patients. For patients in Cohort 1, the pre-dose assessments of Study A4250-008 can be from Study A4250-005.
 
Baseline 2 will be used in all analyses unless otherwise specified.

Baseline for serum bile acids change from baseline	
Baseline 1 is defined for patients in Cohort 1 and will be calculated as the average of last 2 values prior to the first dose in Study A4250-005. If only one non-missing value is available, it will be used as baseline.
 
Baseline 2 is defined as follows:
 
Cohort 1: the average of the last 2 values before the first dose of study drug in Study A4250-008. In general, these 2 values are the values of the last 2 assessments of Study A4250-005. If pre-dose assessments are collected in Study A4250-008 for a patient, then the values of pre-dose assessments in Study A4250-008 will be considered first and used to calculate the baseline. These 2 values need to be taken from 2 consecutive scheduled visits or unscheduled visits. If only one value is available from 2 consecutive scheduled visits or unscheduled visits, then that value will be used as baseline.
 
Cohort 2: the average of last 2 values prior to the first dose in Study A4250-008. If only one non-missing value is available, it will be used as baseline.
 
Baseline 2 will be used in all analyses unless otherwise specified.

End value for serum bile acids change from baseline	The end value is the average of the values at Weeks 70 and 72 after the start of treatment. (Appendix B). If one value is missing, then the non-missing value will be used as the end value. If both values are missing, then the end value is missing.

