AM & PM baseline, daily, weekly, and monthly score (scratching, itch severity)	
For both the Albireo ObsRO scratching item and the Albireo PRO itch severity score:
 
A daily AM & PM score will be averaged from the 2 ratings for each day. A daily score will be considered missing if both assessments are missing.
 
A weekly score will be calculated by averaging all non-missing AM and PM scores in a week. A weekly score will be considered missing if ≥ 8 out of 14 assessments in a week are missing.
 
A monthly score will be calculated by averaging all non-missing AM and PM scores in a month (28 days). A monthly score will be considered missing if ≥ 29 out of 56 assessments in a month are missing.
 
An average score of AM & PM at each visit after Week 24 will be calculated by averaging all non-missing AM and PM scores between 2 visits with analysis windows applied (Appendix B). 50% rule is applied based on the number of planned assessments.
 
All non-missing AM scores from the period of 14 days before or on the first dose day of study medications, and all non-missing PM scores from the period of 14 days before the first dose day of study medications will be averaged as the AM & PM baseline score. Baseline score will be considered missing if ≥ 15 out of 28 assessments in the 14 days are missing. Rounded baseline score will be used for the analysis.
 
One thing of note:
 
Inclusion criteria No. 4 in Study A4250-005:
 
Cohort 1: Patient must have history of significant pruritus and a caregiver-reported observed scratching in the eDiary average of ≥ 2 (on 0 to 4 scale) in the 2 weeks prior to randomisation in Study A4250-005.
 
Inclusion criteria No. 4 in Study A4250-008:
 
Cohort 2: Patient must have history of significant pruritus and a caregiver-reported observed scratching or patient reported itching (for patients > 18 with no caregiver-reported observed scratching) in the eDiary average of ≥ 2 (on 0 to 4 scale) in the 2 weeks prior to the screening/inclusion visit (Visit 1) in Study A4250-008.
 
The pruritus score for purposes of establishing eligibility was calculated by taking the average of the worse of the two scores for each day. The values for week one were averaged and the values for week 2 were averaged. The two weekly averages were then averaged to provide a single score. If this score was ≥ 2 the pruritus eligibility requirement was met. The calculation of pruritus eligibility score is different from the calculation of the baseline pruritus score defined in the SAP.

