Baseline for proportion of responders for pruritus scores	
Baseline 1 is defined as the average of all non-missing daily scores from 14 days prior to the first dose of study drug in study A4250-005.
 
Baseline 2 is defined as the average of all non-missing daily scores from 14 days prior to the first dose of study drug in study A4250-008 (For patients in Cohort 1, the pre-dose assessments of Study A4250-008 can be from Study A4250-005).
 
Baseline score will be considered missing if ≥ 8 out of 14 assessments in the 14 days are missing. The unrounded baseline score will be used for the analysis.

Derivations for Safety Parameters	
AE duration (days)	AE end date–AE start date + 1
TEAEs	An AE (classified by preferred term) occurring during the treatment period and within 28 days follow-up after the last dose that a) has a start date on or after the first dose date of study drug, or b) has a start date before the date of the first dose date of study drug, but worsened in severity on or after the date of the first dose date of study drug. If an AE started in Study A4250-005 and was ongoing at the time of enrolment in Study A4250-008, the AE will not be considered a TEAE unless it worsens in severity on or after the date of the first dose date of study drug.

AE: adverse event; BMI: body mass index; CRF: case report form; eDiary: electronic diary; ObsRO: observer-reported outcome; PFIC: progressive familial intrahepatic cholestasis; PRO: patient-reported outcome; SAP: statistical analysis plan; TEAEs: treatment-emergent adverse events

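### For Cohort 2 and for Cohort 1 Baseline 1, the scratching baseline is taken from the diary days on which patients qualified, so the test of change against zero is tilted towards improvement by an unknown amount

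*SAP*

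**What the plan says.** Section 9.6.3, on the primary endpoints: "Change from Baseline 1 and 2 in monthly scratching severity score to end of the 72-week treatment in Study A4250-008 will be analysed by using" a 1-sample t-test or Wilcoxon signed rank test. It adds: "Baseline 1 will only be used for patients in Cohort 1 who were on odevixibat in Study A4250-005".

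**Baseline windows.** Section 9.6.3 says: "AM scores from the period of 14 days before or on the first dose day in Study A4250-008 will be averaged as AM baseline". The PM baseline uses the 14 days before the first dose day. The general rule in Appendix A is: "Baseline 2 is defined as the last value prior to the first dose in Study A4250-008 for all patients". For the diary, Baseline 1 is spelled out only in the responder row of Appendix A, with reference to A4250-005: "Baseline 1 is defined as the average of all non-missing daily scores from 14 days prior to the first dose of study drug in study".

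**Eligibility windows.** The eligibility note in Appendix A, Table 3 requires of Cohort 2, in A4250-008, a score "in the eDiary average of ≥ 2 (on 0 to 4 scale) in the 2 weeks prior to the screening/inclusion visit (Visit 1) in Study". For Cohort 1 it sets the same threshold over the 2 weeks before randomisation in A4250-005. The eligibility score averages the worse of the two daily scores; the note says that this differs from the baseline score.

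**Screening.** Section 3.1 allows rescreening: "Patients not fulfilling inclusion/exclusion criteria after 3 attempts were not allowed to rescreen". It also says: "Cohort 2 patients and/or caregivers were instructed to complete the eDiary during the Screening period". Screening Visit 1 falls on Days -56 to -35.

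**The concern.** A patient whose true level lies near the threshold is more likely to qualify in a bad fortnight than in a typical one. If that same fortnight is the baseline, the baseline is on average too high for the selected group. Later scores then drift back without treatment. Zero mean change is therefore not what one expects from an inactive drug, yet it is the null of the planned test. Repeat screening can strengthen the effect, because a patient who fails on pruritus may get another chance at a bad fortnight.

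The study has no concurrent control, so nothing in it separates this drift from a drug effect. A small p-value for scratching, reported under the primary endpoint analyses, would be read as evidence of efficacy. The responder summary uses the same kind of 14-day baseline. So does the positive-assessment summary, through its drop-from-baseline criterion.

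**Working it through.** **1. Which comparisons overlap.**

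| Comparison | Days used for eligibility | Days used for baseline | Overlap |
|---|---|---|---|
| Cohort 2, Baseline 2 | 2 weeks before Visit 1 (Day 1) of A4250-008 | 14 days before first A4250-008 dose | Essentially complete |
| Cohort 1 odevixibat, Baseline 1 | 2 weeks before A4250-005 randomisation | 14 days before first A4250-005 dose | Essentially complete |
| Cohort 1, Baseline 2 | As the row above | 14 days before first A4250-008 dose | None; normally 24 weeks later |

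The second row assumes that the scratching test uses the same Baseline 1 window as the responder row. Some early A4250-005 withdrawals reached A4250-008 after at least 12 weeks rather than 24, but no diary threshold is stated for their Baseline 2 days.

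**2. Form of the bias.** Write a fortnight's average as T + P + e, where T is the patient's stable level, P a fortnight-specific shift and e the averaged daily noise. With no drug effect and an independent end period, the expected change is -E(P + e | patient qualified). This is negative when selection and baseline share the same days, and zero when they do not.

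**3. Size.** The SAP gives no figure for this test. Its only power figure (Section 5, 89% to 96%) concerns surgical or death events. It is reproduced by an exact binomial calculation (0.898 at n=48, 0.966 at n=60) and has no bearing here.

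Simulation, with no drug effect:
- From the SAP: scores 0 to 4; entry if the 14-day mean of the worse daily score is at least 2; baseline the 14-day AM/PM average; a 28-day endpoint month; n=60, the planned size of Cohort 2.
- Assumed: integer scores, between-patient SD 0.7, diary-entry SD 0.7, period SD 0 to 0.8, mean of the screened population 1.5 to 3.0, one screening attempt, two-sided 5% t-test.

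Mean change in points, and rejection rate, when baseline and eligibility days coincide:

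| Screened mean | Period SD 0 | 0.3 | 0.5 | 0.8 |
|---|---|---|---|---|
| 1.5 | -0.026; 20% | -0.119; 56% | -0.259; 86% | -0.488; 97.5% |
| 2.0 | -0.013; 9% | -0.067; 21% | -0.154; 44% | -0.333; 76% |
| 2.5 | -0.006; 6% | -0.032; 10% | -0.082; 18% | -0.199; 37% |
| 3.0 | -0.002; 5.5% | -0.012; 6% | -0.035; 7% | -0.103; 14% |

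Where the inflation is material, practically all rejections are for improvement. At mean 2.0 and period SD 0.5, rejection is 25% with n=30 and 35% with n=48. With a later, separate baseline window, as for Cohort 1 Baseline 2, mean change lies between -0.010 and +0.006 and rejection between 4.5% and 5.9% in every setting.

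**4. Rescreening.** With diary-entry SD 0.6, period SD 0.3 to 0.5 and screened mean 1.75 to 2.5, one attempt gives -0.03 to -0.21 points and 8.5% to 68% rejection. Up to three attempts at the pruritus threshold give -0.05 to -0.28 points and 12% to 90%.

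**5. Would an earlier baseline help?** At mean 2.0 and period SD 0.5, a 14-day window before the eligibility window gives about 0.00 points and 5% rejection if fortnights are independent. If the two adjacent fortnights correlate at 0.5 it gives -0.07 and 12%; at 0.8, -0.11 and 24%. The present baseline gives -0.15 and about 44%.

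**The case against.** The strongest objection is that Section 5 plans no formal hypothesis testing, no alpha is set for these tests, and Section 9.6.1 calls the analysis mainly descriptive. No confirmatory claim can fail. That stands, and it limits the consequence to p-values and mean changes that mislead. It does not remove the bias from the mean change itself, and Section 9.6.3 still prescribes the tests.

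The size may also be small. Cohort 2 required a history of significant pruritus, and at a screened mean of 3.0 the inflation is slight. Even 0.3 points is under a third of the 1.0-point threshold for meaningful change in Section 9.6.4, so a large observed fall could not be explained this way. Both points stand. Section 3.1 does not say how often patients were rescreened for pruritus, so the three-attempt figures are an upper case.

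The eligibility score is not the baseline score. This is true, but both come from the same diary entries, so the difference changes the size of the bias and not its direction.

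A reader might infer three stronger things that the SAP does not support:
- That every scratching test is affected. Cohort 1 Baseline 2 is not taken from an eligibility window.
- That every patient had a baseline of at least 2. The threshold was on the worse daily score; in the simulations 5% to 47% of qualifying patients had an average baseline below 2.
- That the test is the only inference on pruritus in Cohort 2. Sections 9.6.3 and 9.6.4 also plan 95% confidence intervals for positive assessments and for responders.

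**Conclusion.** The point holds for Cohort 2 with Baseline 2, for Cohort 1 odevixibat patients with Baseline 1, and for any Overall column that includes Cohort 2. There, zero change is not the expectation without drug effect, and the bias is favourable to odevixibat.

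Its size cannot be fixed from the SAP. In most settings tried it is about -0.01 to -0.3 points; the extreme corners reach -0.002 and -0.49. Rejection at n=60 runs from near 5% to well above 50%. These figures rest on assumed variance components and an assumed mean of the screened population. The rejection rates also rest on n=60; the SAP does not give the size of the Cohort 1 odevixibat group. The effect on the responder and positive-assessment summaries was not quantified.

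It would go too far to say that the type I error is far above 5%, or that an observed improvement is an artefact. The supported conclusion is that a significant result in these comparisons cannot by itself be read as a drug effect.

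**What to change.** 1. Keep the current baseline as the main analysis, for continuity with the two interim analyses in Section 6.
2. For Cohort 2, add a sensitivity analysis of the scratching change, the responder summary and the positive-assessment summary. Take its baseline from screening diary days before the 14-day eligibility window, as early as the data allow, with the same 50% rule. Show both sets of results side by side.
3. State in Section 9.6.3 that p-values for Cohort 2 Baseline 2, Cohort 1 Baseline 1 and the Overall column are descriptive and include regression to the mean.
4. For Cohort 1 Baseline 1, refer to the integrated analysis for a placebo reference. Do not plan one here: Section 10 says that A4250-008 did not have post-baseline A4250-005 data.

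The cost is SAP wording and one added derivation from diaries that Cohort 2 was told to complete in Screening. The SAP does not say how many usable days precede Day -14, so some patients may have too few entries. The added baseline is older, and it reduces the bias rather than removing it if adjacent fortnights are correlated.
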